10.1 Study Timetable

Table 10.1 Study Timetable
(Weekly Details Found in Visit Schedules – Tables 4.1 & 4.2)

Activity	Duration (Avg. min.)	Screening/ Baseline		Phase 1 SMM	Phase 1 EMM		Phase 2 SMM	Phase 2 EMM		
Screening Assessments	Where Applicable		R A N D O M I Z A T I O N			R A N D O M I Z A T I O N				
Informed Consent	25	X								
Inclusion/Exclusion		X								
Randomization					X		X		X	X
Demographics	5	X								
CIDI/Substance Use Diagnosis	40	X								
Concomitant Treatment (including medications and psychosocial)	8	X			X		X		X	X
Safety Assessments										
Medical & Psychiatric Evaluation	45	X								
Vital Signs	5	X			X		X		X	X
Lab Tests (Chemistry, Hematology, Urinalysis, LFTs)	10	X			X		X		X	X
Pregnancy Test	See Labs	X			X		X		X	X
Adverse Events	5				X		X		X	X
Serious Adverse Event					As needed		As needed		As needed	As needed
COWS	5	X			X		X		X	X
Efficacy Assessments										
Substance Use Report – Baseline	15	X			X		X		X	X
Substance Use Report – Follow-up	5									
VAS-Craving	1	X			X		X		X	X
Urine Drug Screen	See Labs	X			X		X		X	X
Pain Assessments										
Brief Pain Inventory	5	X			X		X		X	X
Beck Depression Inventory II	10	X			X		X		X	X
Pain & Opioid Analgesic Use History	10	X		X	X		X	X		
SF-36	10	X		X	X		X	X		
Other Assessments										
CIDI/Depression-PTSD Diagnosis	30	X								
Fagerstrom Test	2	X		X	X		X	X		
Locator Form	5	X		X	X		X	X		
ASI Lite	35	X		X	X		X	X		
Risk Behavior Survey	5	X								
Treatment										
BUP/NX Induction Visit	60			X	X		X	X		
SMM session (including BUP/NX dosing)	15-20			X	X		X	X		
EMM session	45				X			X		

10.2 Protocol Specific Assessments

10.2.1 Laboratory Tests (e.g., Pregnancy Test, Liver Profile)

- *Pregnancy Testing:* Female participants of child-bearing potential will be required to have a negative pregnancy test (urine hCG,) prior to induction, and monthly thereafter while receiving BUP/NX. Buprenorphine is a Pregnancy Category C Drug. Female participants of childbearing potential will also be expected to practice acceptable birth control. Women who become pregnant will be withdrawn from the study, tapered off BUP/NX, and referred for opioid replacement therapy at the CTP or to another local treatment provider.
- *Blood Chemistries and Liver Function Tests:* Blood will be collected in appropriate vacutainer tubes, and handled according to standard procedures. Quantitative analysis will be performed for a standard chemistry and liver function profile. The following analytes will be recorded on the appropriate case report form: sodium, potassium, chloride, bicarbonate, glucose, creatinine, albumin, total protein, calcium, cholesterol, triglycerides, phosphorous, alanine aminotransferase (ALT/SGPT), aspartate aminotransferase (AST/SGOT), gamma glutamyltranspeptidase (GGT), total bilirubin, alkaline phosphatase (ALP), and blood urea nitrogen (BUN). Subjects with LFTs > 5X upper limit of normal range at screening will be ineligible for the study.
- *Hematology:* Blood will be collected in appropriate vacutainer tubes, and handled according to standard procedures. Quantitative analysis will be performed for a standard hematology profile. The following analytes will be recorded on the appropriate case report form: hemoglobin (Hgb), hematocrit (Hct), RBC, WBC, neutrophils, lymphocytes, monocytes, eosinophils, basophils, platelets.
- *Urinalysis:* Urine will be collected and analyzed for a standard urinalysis profile. The following results will be recorded on the appropriate case report form: specific gravity, pH, color, appearance, glucose, bilirubin, ketones, occult blood, protein, nitrite, leukocyte esterase.
- *Urine drug screen:* Urine will be collected, analyzed, and recorded on the appropriate CRF for the following analytes: oxycodone, benzodiazepines, THC, methadone, cocaine, amphetamine, methamphetamine, propoxyphene, and the Opiate 300 group analytes (morphine, heroin, and codeine).

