7.2 Baseline Assessment

Baseline assessments will include a comprehensive evaluation of demographics, drug history and lifetime diagnoses, addiction severity, concomitant medications (over the counter or by prescription), withdrawal status, medical and psychiatric status, assessment of HIV risk, and pain. Medical status will be determined by medical history, physical examination, and clinical laboratory evaluations (including complete blood count, chemistry profile, liver function profile, urinalysis, and urine screen for drugs of abuse). Vital signs will also be obtained.

All females of child-bearing potential will be required to have a pregnancy test prior to receiving their first dose of investigational agents. All female participants of childbearing potential will be required to practice acceptable birth control (e.g., oral or depot contraceptives, foam, sponges, and/or condoms). Birth control methods will be documented on the CRF. Female participants who become pregnant will be withdrawn from the study and provided immediate access to methadone maintenance services at the CTP or another local treatment provider. Women refusing methadone maintenance will be referred to another local provider.

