7.4 Treatment Discontinuation & Study Termination

7.4.1 Participant-Initiated Discontinuation

Participation in this study is voluntary. If the participant chooses not to receive study medication, SSM, and/or EMM (i.e. individual drug counseling), that will not affect his/her relationship with that particular study site, or his/her right to health care or other services. The participant is free to withdraw his/her consent and discontinue participation in study treatments and/or study research at any time without prejudice to his/her future health care.

Discontinuation from study treatment refers to the discontinuation of one or more of the following:

- BUP/NX
- SMM
- EMM

In most cases, even if treatment is discontinued, site staff will continue to follow participants for the purposes of collecting research and safety information. Discontinuation of study treatment (either participant initiated, investigator initiated, or mutually agreed) and discontinuing research visits should be viewed as separate events in most cases and negotiated as such with participants.

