7.4.2 Investigator-Initiated Discontinuation

The investigator may discontinue study medication, EMM, and/or SMM treatment if circumstances arise, including but not limited to:

- Adverse reaction to study medication that require removal from the medication (e.g. allergic reaction)
- A change in medical status that makes it unsafe for a participant to continue participating
- A participant becomes ill during the study
- Serious behavioral problems or negative behaviors such as selling drugs at the study site

Participants discontinued from study treatment will be provided appropriate referrals to alternative treatments in the area by study personnel.

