7.4.2.2 Procedures for Discontinuation

If EMM, SMM, or BUP/NX treatment is discontinued, either participant-initiated or investigator-initiated, the participant may continue to participate in the other study treatments; except if SMM is discontinued, he/she can not continue to receive BUP/NX. In most cases when all components of the participant's study treatment is discontinued, only study research visits will be expected from that point forward. Occasionally, a participant who has discontinued from study treatment may elect to return to one or more components of treatment. In this case, if the participant remains appropriate and within the treatment window based on the randomization date, the participant may be allowed to return to treatment. This may occur in Phase 1 or Phase 2 (up to the final day of the week 8 SMM visit window in Phase 2). As such, if a participant discontinues BUP/NX in Phase 2 and wishes to be restarted on BUP/NX, re-induction of BUP/NX can occur in Phase 2 until week 8 only.

Upon completion of the tapering phase, or in cases of early dropout, participants may continue in treatment at the CTP (if available), or may be referred to available local treatment resources. In the event that any participant desires additional pharmacological treatment for his/her opiate dependence, or if the study staff finds that additional treatment is clinically indicated, the site will refer the participant to a local provider of methadone or buprenorphine.

Participants whose clinical status worsens substantially during the study (e.g., increased opioids use, needle use, more dangerous behaviors such as overdose) may be referred to other treatment options; for instance, participants will be told about methadone maintenance as well as more intensive psychosocial treatment, or participants who relapse to regular opioids use in the context of severe and/or worsening pain may be referred to a pain clinic if clinically appropriate. All such participants will remain part of the study and will continue to be followed for research. A decision as to whether it is appropriate for such participants to continue with study treatment will be made by the local study medical clinician in consultation with the Lead Investigator (LI) or designee.

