7.4.2.4 Study Termination

Study termination refers to the end of all study treatment AND study research data collection (e.g. final visits in Phase 1 and Phase 2), and is treated separately from treatment discontinuation. Early study termination may take place if a participant withdraws his/her consent to participate. The reason for study termination will be noted on the appropriate study termination CRF.

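### Pregnancy leads to withdrawal from the study rather than from study treatment, which gives up scheduled safety and research visits without a stated reason

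*Protocol*

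**What the plan says.** Two sections of the protocol deal with pregnancy during the trial. Section 10.2.1: "Women who become pregnant will be withdrawn from the study, tapered off BUP/NX, and referred for opioid replacement therapy". Section 7.2: "Female participants who become pregnant will be withdrawn from the study and provided immediate access to methadone maintenance services".

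Section 7.4 sets out how participants leave. Treatment discontinuation means stopping BUP/NX, SMM or EMM. The other exit is defined in Section 7.4.2.4: "Study termination refers to the end of all study treatment AND study research data collection". That section keeps it apart from treatment discontinuation and gives one ground for its happening early: "Early study termination may take place if a participant withdraws his/her consent to participate".

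For participants who stop treatment, Section 7.4.1 says: "In most cases, even if treatment is discontinued, site staff will continue to follow participants for the purposes of collecting research and safety information". Section 7.4.2 lists, among the reasons for an investigator to stop treatment: "A change in medical status that makes it unsafe for a participant to continue participating". Section 7.4.2.2 says of participants who have stopped all study treatment that, in most cases, "only study research visits will be expected from that point forward".

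**The concern.** A pregnant participant has been randomised and exposed to a drug that Section 10.2.1 itself labels Pregnancy Category C. Under the general rules of Section 7.4, an unsafe change in medical status would stop her treatment and leave her visits in place. The pregnancy rule instead takes her out of the study, and the protocol does not say why.

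At stake are adverse events, which under Section 12.2.1.4 are elicited at visits, and the observed secondary outcomes of a randomised participant. The two pregnancy sections also describe the treatment step differently, so a site cannot tell from the text whether a taper on study drug is required.

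**Working it through.** The protocol gives no figure to reproduce on this point. The check is a comparison of text, followed by a count of visits.

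**1. Which exit is meant.** Section 7.4 has only the two exits described above. Sections 7.2 and 10.2.1 speak of the study, not of study treatment, so termination under Section 7.4.2.4 is the natural reading. It remains an inference: the defined term is not used, and pregnancy is not named in Section 7.4.2.4.

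**2. What the protocol does elsewhere.**
- Sections 7.4.1 and 7.4.2.2: follow-up normally continues after treatment stops. Participants who worsen, including by overdose, stay in the study.
- Section 7.4.2.1: sites try to assess status at every follow-up point.
- Section 11.2.4: every effort is to be made to assess all patients in both phases.
- Section 12.2.1.6: someone who voluntarily leaves treatment is asked to continue at least limited scheduled evaluations.

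No section keeps pregnant participants in follow-up, and none gives a reason for treating them differently.

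**3. The two pregnancy rules compared.** Section 10.2.1 has withdrawal, a BUP/NX taper and referral for opioid replacement. Section 7.2 has withdrawal and immediate methadone access, with no taper.

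**4. Visits lost.** Inputs, from Section 1.2.2.4 and Tables 1.1 and 1.2: Phase 1 data are collected weekly in Weeks 1-4, then at Weeks 6, 8, 10 and 12. Phase 2 data are collected weekly in Weeks 1-16, then at Weeks 18, 20, 22 and 24. Section 10.2.1 requires monthly pregnancy tests while on BUP/NX, read here as every four weeks.

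Phase 2 formula: visits lost = (16 - week of positive test) + 4.

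| Positive test | Visits lost |
|---|---|
| Phase 1 Week 4 | 4 (Weeks 6, 8, 10, 12) |
| Phase 2 Week 4 | (16 - 4) + 4 = 16 |
| Phase 2 Week 8 | (16 - 8) + 4 = 12 |
| Phase 2 Week 12 | (16 - 12) + 4 = 8 |
| Phase 2 Week 16 | (16 - 16) + 4 = 4 |

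**5. What is not lost.**
- Primary outcome: the analysis includes everyone randomised (Section 11.2.3). Anyone leaving the study before Week 12 is a failure in Phase 1 (Section 11.3.3.3) and not substantially improved in Phase 2 (Section 11.4.3.3). The planned 648 and 324 and the power are unchanged.
- Safety: Section 12.2.1.4 follows serious and study-related events beyond the end of the study. That covers events already elicited. Routine detection of new ones depends on visits.
- Urine results: Section 11.2.4 imputes a missing urine as positive when entry into an opiate treatment programme is known. Part of this series would therefore be filled by rule rather than observed. The protocol states no such rule for craving, depression or quality of life.

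**The case against.** The strongest defence is that this is a deliberate, specific rule beside a general one that allows exceptions. Sections 7.4.1 and 7.4.2.2 both qualify continued follow-up as holding in most cases. Pregnancy is exclusion criterion 13 (Section 5.1.1.2), so ending participation is coherent, and both pregnancy sections agree on withdrawal. This stands as far as it goes: a reader might infer that the protocol contradicts itself, and it does not. The defence does not supply a reason for the exception or undo the loss of visits.

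It can also be said that withdrawal need not mean termination, since the protocol uses such words loosely. Section 11.4.3.3, for example, counts non-compliance as a way of discontinuing the study. That makes the reading less certain, but no text supports the alternative of continued visits.

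A reader might further infer that the taper in Section 10.2.1 cannot be carried out, because terminating the study ends SMM and Section 7.4.2.2 says "except if SMM is discontinued, he/she can not continue to receive BUP/NX". The documents do not force this. The sentence in Section 10.2.1 is a list, not a stated order, and the taper may come before withdrawal.

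Finally, the scheduled visits recover adverse events and outcome measures. They do not add follow-up of the pregnancy itself, and the benefit should not be described that way.

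**Conclusion.** The point holds as a minor one. As most naturally read, Sections 7.2 and 10.2.1 end data collection in participants whom the protocol's general approach would keep under observation, with no reason given, and they disagree on the taper. The loss per affected participant is 4 scheduled visits after a positive test at Phase 1 Week 4, and between 4 and 16 in Phase 2 depending on when the test turns positive. This rests on equating withdrawal with study termination and on four-weekly testing.

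No total is given, because the protocol states neither a pregnancy rate nor the proportion of women. A reader might infer bias in the primary comparison, or that all safety follow-up stops. Neither is supported: primary status is assigned by rule, and serious and study-related events continue to be followed.

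**What to change.** Use the same wording in Sections 7.2 and 10.2.1, replacing withdrawal from the study with discontinuation of study treatment under Section 7.4.2, and state that:

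- BUP/NX is tapered, or the participant is transferred to opioid replacement therapy, with SMM continuing until the last study dose;
- she is not eligible for Phase 2 randomisation or further BUP/NX treatment (exclusion criterion 13);
- scheduled research and safety visits continue unless she withdraws consent.

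One detail should be settled in the same edit. Section 11.4.3.3 covers participants who complete 12 weeks of Phase 2 treatment and those who leave the study earlier, but not someone who stops treatment and stays in follow-up. Saying that she is still counted as not substantially improved keeps the primary outcome as it is now.

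The cost is a protocol amendment with IRB review (Section 16.1) and, per affected participant, the visits counted above, which are already in the schedule.

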10.2.2 Clinical Assessments (e.g. Medical History and Physical Exam)

The study medical clinician (or other qualified medical study staff) will complete a physical examination to help determine eligibility. The physical exam will also ensure that there are no medical concerns regarding participation and to gather baseline information about the participant's health. The physical examination will be repeated at the end of the study (last study visit). Pertinent laboratory tests (LFTs, CBC, chemistry) will be reviewed at the visits specified in Table 4.1 on page 4-5 and Table 4.2 on page 4-6. See the *Operations Manual* for guidance on laboratory value parameters. Participants with abnormal laboratory values will be notified and counseled to seek medical evaluation and care.

For participants receiving opioids for chronic pain, the study medical clinician will consult with the participant's prescribing physician to ensure that the participant is appropriate to participate in this protocol; e.g., that the participant's pain is not due to an underlying malignancy or that further diagnostic testing is not needed to determine the source of the pain.

10.2.3 Efficacy Assessments

10.2.3.1 Urine Drug Testing

Urine samples will be collected and analyzed for drugs of abuse prior to dispensing medication. All urine specimens will be analyzed by staff using drug test cups with temperature-controlled monitoring. These cups will be provided by a central supplier to all study sites. OxyImmunoassay and drug screen cards will be used to identify the following substances: oxycodone, benzodiazepines, THC, methadone, cocaine, amphetamine, methamphetamine, propoxyphene, and the Opiate 300 group analytes (morphine, heroin, and codeine). Other drugs may be detected by these analytes at high concentrations. For example, hydrocodone may be detected under the oxycodone test at high concentration levels. The cards will be provided to all study sites from a central supplier.

Urine will be collected at baseline just prior to BUP/NX induction, at each of the weekly visits thereafter, and at each follow-up visit. Urine screens for BUP will be available at Weeks 10 and 12 in Phase 1 and Weeks 22 and 24 in Phase 2. The urine screens for BUP will be used to monitor whether participants defined as "successes" at the end of Phase 1 and "substantially improved" at the end of Phase 2 (in both instances, when they are supposed to be off buprenorphine) are, in fact, taking buprenorphine that they have obtained outside the study.

The results will be recorded on the appropriate CRF.

10.2.3.2 Substance Use Report

Drug use data will be collected in conjunction with weekly medical management visits. A calendar technique similar to the Timeline Followback will be used to fill in each day since the last visit, which helps to fill in missing data in case of missed visits. Baseline data collection will review past 30 days of substance use. The use of opioids, other drugs of abuse, and alcohol will be recorded. A urine drug screen will be performed at each of these visits as well.

10.2.3.3 Clinical Opiate Withdrawal Scale (COWS)

The COWS is an 11-item interviewer-administered questionnaire designed to provide a description of signs and symptoms of opiate withdrawal that can be observed directly in the participant (e.g., sweating, runny nose, etc.). The COWS will be completed at each clinic visit during treatment.

10.2.3.4 Visual Analog Scales (VAS)

Five visual analog scales will be completed at each clinic visit during treatment to assess craving for opiates. The VAS will also be collected at all follow-up visits in Phase 1 and at the Week 20 and Week 24 follow-up visits in Phase 2.

10.2.4 Safety Assessments

Safety assessments will consist of physical examination, vital signs, laboratory tests, pregnancy tests, adverse event reporting, and concomitant medications use.

Adverse events (AEs) will be monitored during the study. An **AE** is defined as any reaction, side effect, or untoward event that occurs during the course of the clinical trial, whether or not the event is considered medication- or study-related or clinically significant. For this study AEs will include events reported by the participant. A new illness, symptom, sign, or worsening of a pre-existing condition or abnormality is considered an AE. Stable chronic conditions, such as arthritis, which are present prior to clinical trial entry and do not worsen are not considered AEs. All AEs must be recorded on the AE CRF (Case Report Form). The AE CRF is also used to record follow-up information for unresolved events reported on previous visits. Each AE will be classified by the study investigator as serious or non-serious and appropriate reporting procedures followed.

Serious adverse events (SAEs) are defined as any fatal event, any immediately life-threatening event, any permanent or substantially disabling event, any event that requires or prolongs hospitalization, any congenital anomaly, or any event that required intervention to prevent one of the above outcomes. This category includes any event that a study investigator or the DSMB judges to be serious or which would suggest a significant hazard, contraindication, side effect, or precaution. For the purposes of this study, admission to a hospital or free-standing residential facility for the treatment of drug dependence (e.g., detoxification or rehabilitation) is not defined as an SAE, but the event will be recorded on the concomitant treatment CRF.

An **unexpected event** is one that is not described with respect to nature, severity or frequency in the current Investigator Brochure, or is standard symptomatology for opioid withdrawal.

10.2.5 Pain and Other Assessments

10.2.5.1 Brief Pain Inventory

The Brief Pain Inventory-SF (BPI; Cleeland & Ryan, 1994) is a 9-item assessment of intensity of pain and interference of pain in life. Originally developed for cancer pain, it is widely used to assess nonmalignant acute and chronic pain (Tan, Jensen, Thornby & Shanti, 2004).

The complete BPI-SF will be collected at baseline and monthly during Phase 1 and Phase 2. For patients identified at baseline and stratified as chronic pain patients, four BPI-SF items will be asked weekly throughout treatment as part of their medical visit for the purpose of monitoring any potential changes in physical pain. In addition to verbal patient report of pain, these items will permit study clinicians to monitor for any clinical deterioration in pain status that may require follow-up and/or referral.

